13.4.2. Primary Analysis of Primary Endpoint

The primary endpoint is change in percentage of UVB-induced apoptotic epidermal cells from Visit 2 (Day 1) (pre-treatment) to Visit 5 (Day 26) (post-treatment). Percentage of UVB-induced apoptotic cells (A^{UVB}) is defined as the number of TUNEL positive cells in the epidermis divided by the number of nuclei in that high powered field. The percentage of UVB-induced apoptotic cells at a visit is defined as the difference between the percentage of apoptotic epidermal cells in the biopsy exposed at the MED ($A^{Day1MED}$) and percentage of apoptotic epidermal cells in the unexposed biopsy ($A^{unexposed}$), for both biopsies taken at the same visit. The change in percentage of UVB-induced apoptotic epidermal cells will be computed as follows for each individual in the study:

$$A_{Day\ 1}^{UVB} = A_{Day\ 1}^{Day1MED} - A_{Day\ 1}^{Day\ 1\ unexposed}$$

$$A_{Day\ 26}^{UVB} = A_{Day\ 26}^{Day1MED} - A_{Day\ 26}^{Day\ 26\ unexposed}$$

$$\text{change in } A^{UVB} = A_{Day\ 26}^{UVB} - A_{Day\ 1}^{UVB}$$

The null and alternative hypotheses for the primary analysis of the primary endpoint are:

H_0 : Mean change in $A^{UVB} = 0$

H_A : Mean change in $A^{UVB} \neq 0$

The statistical hypotheses outlined above for the mean change in A^{UVB} will be evaluated in the PP1 population using a two-sided Wilcoxon signed-rank test at a Type 1 error rate of 0.05.

13.4.3. Supportive Analyses of the Primary Endpoint

The primary hypothesis will also be evaluated in the PP2 population. In addition, depending on findings, exploratory analyses may be considered post hoc.

13.4.4. Analyses of Secondary Endpoints

The PP1 population will be used for evaluation of photosensitivity and disease activity measures. For each secondary endpoint, the null hypothesis is that there is no change in the parameter of interest from pre- to post-treatment time points. All secondary inferential analyses are considered supportive; p-values will be presented without adjustment for multiple comparisons.

Analysis of secondary safety endpoints will be conducted using the safety population.

13.4.4.1. Photosensitivity parameters

The following analyses of these secondary endpoints will support the primary objective to evaluate the impact of tofacitinib on photosensitivity parameters.

- **Change in MED due to UVB from Visit 2 (Day 1) to Visit 5 (Day 26):** MED is an ordinal endpoint. Shifts in MED levels from pre- to post-treatment will be evaluated using the McNemar-Bowker test for symmetry.
- **Change in UVB-induced expression of inflammatory genes in skin from Visit 2 (Day 1) to Visit 5 (Day 26), based on enumeration of RNA transcripts:** The mean change will be evaluated using a two-sided Wilcoxon signed-rank test.

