Study Design	
This is a single-arm, multi-site, proof-of-concept study of 10 participants with CLE. Consenting individuals meeting all entry criteria will undergo 25 days of treatment with tofacitinib (11 mg orally (PO) daily) with evaluation of UVB-mediated cutaneous apoptosis and ancillary mechanistic studies before and after treatment. Post-screening study visits will be conducted on Days 0 (Visit 1), 1 (Visit 2), 14 (Visit 3), 25 (Visit 4), 26 (Visit 5), and 40 (Visit 6) to (1) evaluate adverse events, vital signs, hematology and chemistry, study drug compliance, medication use, and disease status, (2) conduct UVB phototesting, and (3) collect skin biopsies and blood samples for mechanistic studies. Tofacitinib will be distributed to eligible participants at Visit 2 (Day 1) and the first dose will be taken on Day 2. The last dose is the morning of Visit 5 (Day 26). Participants are allowed to continue on their stable background therapies for lupus according to Section 7.1.2, Other Permitted Concomitant Medications. Please refer to Section 8.1.1, Exceptions to Visit Windows, and Section 6.6, Resumption of Investigational Product, for more information regarding delays to visits 4 and 5.

Primary Endpoint	
Primary Endpoint
 
The change in percentage of UVB-induced apoptotic epidermal cells from Visit 2 (Day 1) (pre-treatment) to Visit 5 (Day 26) (post-treatment). Percentage of UVB-induced apoptotic cells at a visit is defined as the difference between the percentage of apoptotic epidermal cells in the UVB-exposed biopsy and percentage of apoptotic epidermal cells in the unexposed biopsy at the same visit. More information can be found in Section 8.5.5, Research Assessments.

Accrual Objective	10 participants completing two phototests at least 3 weeks apart.
Study Duration	This study is estimated to last 1 year.
Treatment Description	Participants will receive a 25-day regimen of tofacitinib 11 mg daily.

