2.1. Hypotheses

In individuals with CLE, a 25-day regimen of tofacitinib will:

- reduce UVB-mediated cutaneous apoptosis,
- reduce UVB-mediated inflammatory gene transcription, and
- increase minimal erythema dose (MED) after UVB exposure.

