8.5.5. Research Assessments

- **Blood for Serum Biomarkers** will be drawn at Visit 1 (Day 0) and Visit 4 (Day 25).
- **Blood for Cellular and Proteomic studies** will be drawn at Visit 1 (Day 0) and Visit 4 (Day 25).
- **UVB Exposure:**
 - A UV Lamp (Ultralite Enterprises Model 36P10A 10-UNV or equivalent device) will be identified by model name and number, and manufacturer at each site. The same device will be used for all phototesting at each site. The UVB dose, based upon the distance from the UV lamp to the participant, will be determined using dedicated photometer and probe prior to each use.

Phototesting will occur at the study site. A photo-barrier template will be placed on non-lesional skin of the participant's exposed lower back/buttock. The template will be placed on the right lower back/buttock for the phototest on Visit 1 (Day 0) and on the left lower back/buttock for the Visit 4 (Day 25) test. UV irradiation will be applied to the template area via a UV Lamp (Ultralite Enterprises Model 36P10A 10-UNV or equivalent device), and every 40 seconds a single template square of the barrier will be covered until all 8 template squares have been covered (i.e., total exposure ranges from 10-80 mJ/cm²).

Before initiating phototesting at Visit 4 (Day 25), the participant should meet all the following criteria:

- The participant must have completed at least 21 days of IP dosing.
 - For individuals whose Visit 4 (Day 25) has been delayed (See Section 8.1.1, *Exception to Visit Windows*), the 21 days starts from the day IP dosing is resumed.
- The participant must confirm that no IP doses have been missed in the prior 7 days. Dosing will be tracked on a paper patient diary and in the EDC (Electronic Data Capture) system.
- The participant must have taken at least 84% of expected daily doses from the day of the first IP dose. Compliance is based on a pill count conducted at Visit 4 (Day 25).

- For individuals whose Visit 4 (Day 25) has been delayed (See Section 8.1.1, *Exception to Visit Window Rules*), compliance should be computed from the day IP dosing is resumed.

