If a participant fails to bring the IP pill bottle(s) back at Visit 4 (Day 25), UVB exposure may proceed during this visit. However, site personnel must confirm at least 84% compliance via a visual pill count prior to the erythema assessment and biopsy at Visit 5 (Day 26). If 84% compliance is not achieved, participant may resume IP dosing. Once the participant has completed appropriate IP dosing, the UVB exposure will be conducted on a site on the lower back, above the original. If the participant does not take the final dose of IP the morning of Visit 5 (Day 26), the erythema assessment and biopsy will still take place, as long as the participant is compliant with their IP dose the 7 days prior to Day 26.

- **Erythema Assessment:**

At Visit 2 (Day 1) and Visit 5 (Day 26), erythema levels for unexposed skin and each template square of the UVB-exposed skin will be quantified using a Chroma Meter (Minolta Model CR-400 or equivalent device). To determine the MED, first compute the average of all the unexposed skin's a* (redness) readings and add 2.5. The lowest exposure with the site's average a* (redness) readings at or above this value is the MED. All skin types (except for Fitzpatrick VI) can be expected to show a response within the planned exposure range[26].

- **Skin Biopsy:** At the indicated time points, 6mm-diameter punch biopsies of nonlesional skin are planned at 3 sites as follows:

1. On Visit 2 (Day 1), 3 biopsy sites on the right buttock include (1) unexposed skin, (2) skin exposed to the 1x MED, and (3) skin exposed to the UVB dose that is 1 step higher than the 1x MED.
2. On Visit 5 (Day 26), 3 biopsy sites on the left buttock will be comparable to those taken on Visit 2 (Day 1), including (1) unexposed skin, (2) skin exposed to the same UVB Dose as the 1x MED from the Visit 2 (Day 1) assessment, and (3) skin exposed to the UVB dose that is 1 step higher than the 1x MED from the Visit 2 (Day 1) assessment. If the 1x MED from the Visit 2 (Day 1) assessment is at the highest UVB dose (80mJ/cm²) or if no erythema is detectable on exposed skin at any dose, then two 4mm biopsies of skin exposed the highest UVB dose will be taken at both Visit 2 (Day 1) and Visit 5 (Day 26).
3. Stitch removal is planned for Visit 3 (Day 14) and Visit 6 (Day 40).

Table 8.2. Schedule of Events

Time Point	Screening	Visit 1	Treatment				Visit 6	Early Termination Visit	Restart Visit ^H	Unscheduled Visit

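### With 10 participants, the McNemar-Bowker test chosen for the change in MED cannot reach significance on the 8-level scale, whatever the drug does

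*Combined protocol and SAP*

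**What the plan says.** Section 2.1 predicts that treatment will "increase minimal erythema dose (MED) after UVB exposure". Sections 2.2 and 13.1 list MED among the three photosensitivity parameters under the primary objective, with UVB-mediated apoptosis and inflammatory gene transcription.

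MED is read from a graded exposure. Under Section 8.5.5, "every 40 seconds a single template square of the barrier will be covered until all 8 template squares have been covered", which gives total exposures from 10 to 80 mJ/cm². The skin biopsy item of the same section also provides for the outcome "if no erythema is detectable on exposed skin at any dose".

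The synopsis sets the accrual objective at "10 participants completing two phototests at least 3 weeks apart". Section 13.4.4 says: "The PP1 population will be used for evaluation of photosensitivity and disease activity measures". For MED, Section 13.4.4.1 states "MED is an ordinal endpoint" and continues: "Shifts in MED levels from pre- to post-treatment will be evaluated using the McNemar-Bowker test for symmetry". It gives no rule for degrees of freedom, no exact version, no pooling of levels and no power. Every other change endpoint with a named test (apoptosis, gene expression, CLASI activity and damage, SLEDAI-2K) uses the Wilcoxon signed-rank test.

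**The concern.** The test does not match the endpoint. McNemar-Bowker asks whether a square table of before-and-after categories is symmetric. It treats each pair of levels as a separate comparison, so a rise from 20 to 30 mJ/cm² and a rise from 50 to 60 mJ/cm² do not reinforce each other. It uses neither the order that the plan itself recognises nor the predicted direction.

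It also relies on a large-sample chi-square reference, yet ten participants are spread over 28 pairs of levels, or 36 if no erythema counts as a ninth level. A unanimous improvement in MED could therefore be reported with a p-value close to 1 and be read as evidence of no effect on one of the three photosensitivity parameters.

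**Working it through.** **Inputs.** n = 10 pairs (synopsis, accrual objective). k = 8 levels, or 9 with no erythema (Section 8.5.5). Two-sided alpha of 0.05 is assumed for MED: Section 13.4.2 gives it for the primary endpoint and Section 13.4.4 sets no other.

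**The plan's own power figure.** Section 13.7 covers only the apoptosis endpoint: at least 93% for a 20-point change with SD 15. This reproduces. Dividing 10 by the Wilcoxon efficiency factor π/3 for the normal gives 9.55, truncated to 9; the noncentral-t power is then 93.7%, the lowest of the four distributions. No figure is given for MED.

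**Upper bound.** The statistic is B = Σ over pairs i<j of (n_ij − n_ji)² / (n_ij + n_ji). Each term is at most n_ij + n_ji, with equality when all shifts in that pair go one way. So B cannot exceed the number of participants who change, and B ≤ 10.

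**Standard degrees of freedom, k(k−1)/2:**

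| Levels k | df | 5% critical value | Smallest p (B = 10) |
|---|---|---|---|
| 3 | 3 | 7.81 | 0.019 |
| 4 | 6 | 12.59 | 0.125 |
| 8 | 28 | 41.34 | 0.9993 |
| 9 | 36 | 51.00 | >0.9999 |

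With all 8 levels, at least 42 participants shifting one way would be needed. If k counts only the levels seen in the data, rejection is impossible from k = 4 upward.

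**More favourable versions, neither specified in the plan.**
- Degrees of freedom equal to the number m of non-empty pairs: with m = 4 all ten must shift one way (p = 0.040); with m = 5 even that gives p = 0.075.
- Exact conditional test: if all ten shift one way, p = 2^(m−10). This is 0.031 for m = 5 and 0.0625 for m = 6.

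**The same data under signed-rank.** If all ten rise one step, exact two-sided p = 2 × 0.5¹⁰ = 0.002, whatever the baseline levels.

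**Simulated power.** The documents give no MED distribution, so every baseline and shift pattern here is an assumption (4,000 replicates each).

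| Scenario | Bowker, df 28 | Bowker, non-empty pairs | Bowker, exact | Signed-rank, exact |
|---|---|---|---|---|
| Baseline spread (SD 1–1.5 steps, or uniform), mean rise 1–3 steps | 0% | 0–7% | 0.3–25% | about 60–100% |
| Very narrow baseline (SD 0.5 step), mean rise 1–3 steps | 0% | 7–38% | 12–73% | 59–100% |
| Baseline uniform over 20–70 mJ/cm²; shifts −1/0/+1/+2 with probability 0.05/0.25/0.45/0.25 | 0% | about 0.2% | not run | 69% |
| Baseline on three adjacent levels (25/50/25%), 90% of participants rise one step | 0% | about 94% | not run | over 99% |

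**The case against.** The strongest reply is that the plan does not say how the degrees of freedom are counted. If only non-empty pairs count, and baseline MEDs lie on two or three adjacent levels with almost everyone moving up one step, power can exceed 90%, as the last row of the table shows. That is correct, so zero power is not a property of every version of the test. It depends, however, on an unstated convention and on a tight cluster of baseline MEDs. The only skin type that Section 8.5.5 sets apart is Fitzpatrick VI, and only as one that may not respond within the exposure range. In every scenario run, signed-rank had more power.

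A second reply is that MED is secondary, that Section 13.4.4 treats such analyses as supportive, and that no decision rule depends on this p-value. This also stands and limits the harm. It does not make the test informative: the p-value will still be reported, under a heading that says these analyses support the primary objective.

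A third point concerns the replacement. Signed-rank uses the size of each step change, and placing no erythema one step above 80 mJ/cm² gives a fixed value to a censored outcome. The eight exposures are evenly spaced, (80 − 10)/7 = 10 mJ/cm², so step size is a reasonable scale. The censoring can be examined with a sign test, which needs only direction.

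**Conclusion.** The concern holds. For the named test with its usual degrees of freedom on the 8-level scale, a significant result is arithmetically impossible: the maximum statistic is 10 against a critical value of 41.34. This rests only on n = 10 and alpha = 0.05, not on any assumed effect or baseline. Counting observed levels only, it remains impossible from four levels upward. Under the two more generous versions, power was at most 7% and 25% for the spread baselines examined, and useful power needed baseline MEDs concentrated on very few levels. Those power figures depend on the assumed distributions; the bounds do not.

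The consequence is confined to inference on MED. The primary endpoint, its test and its power are untouched. As written, though, a non-significant MED result would say nothing about whether tofacitinib changes MED.

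**What to change.** In Section 13.4.4.1, replace McNemar-Bowker with an exact two-sided Wilcoxon signed-rank test on the within-participant change in MED dose step. State that the exact permutation distribution is used with ties (the changes are small integers), and say how zero changes are handled. Define no erythema up to 80 mJ/cm² as a ninth step ranked above 80. Show the before-and-after shift table descriptively. An exact sign test could be added as a sensitivity analysis for participants with no erythema at either visit.

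The cost is a few lines of SAP text, with no new data, visits or procedures. The change should be made before any post-treatment MED data are examined; made later, it would look driven by the results.

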13.4.4.2. Disease activity

- **Changes in CLASI activity score, CLASI damage scores, and SLEDAI-2K total scores from Visit 1 (Day 0) to Visit 4 (Day 25):** For each endpoint, the mean change will be evaluated using a two-sided Wilcoxon signed-rank test.

13.4.4.3. Safety

- Clinical laboratory values will be summarized using descriptive statistics. In addition, individuals with a laboratory value that increases during the study by 1 or more severity grades per NCI-CTCAE will be identified and tabulated.
- Treatment-emergent AEs and SAEs will be summarized by severity, by relationship to study drug, and by MedDRA Organ Class and Preferred Term.

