3.1. Description of Study Design

This is a single-arm, multi-site, proof-of-concept study of 10 participants with CLE. Consenting individuals meeting all entry criteria will undergo 25 days of treatment with tofacitinib (11 mg orally (PO) daily) with evaluation of UVB-mediated cutaneous apoptosis and ancillary mechanistic studies before and after treatment. Post-screening study visits will be conducted on Days 0 (Visit 1), 1 (Visit 2), 14 (Visit 3), 25 (Visit 4), 26 (Visit 5), and 40 (Visit 6) to (1) evaluate adverse events, vital signs, hematology and chemistry, study drug compliance, medication use, and disease status, (2) conduct UVB phototesting, and (3) collect skin biopsies and blood samples for mechanistic studies (See Figure 1).

Tofacitinib will be distributed to eligible participants at Visit 2 (Day 1) and the first dose will be taken on Day 2. The last dose is the morning of Visit 5 (Day 26). Participants are allowed to continue on their stable background therapies for lupus according to Section 7.1.2, *Other Permitted Concomitant Medications*.

Please refer to Section 8.1.1, *Exceptions to Visit Windows*, and Section 6.6, *Resumption of Investigational Product*, for more information regarding delays to visits 4 and 5.

[figure not shown]

Figure 1. Study Schematic

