12.2.2. Suspected Adverse Reaction

Any adverse event for which there is a reasonable possibility that the investigational drug [or investigational study therapy regimen] caused the adverse event. For the purposes of safety reporting, 'reasonable possibility' means there is evidence to suggest a causal relationship between the drug and the adverse event. A suspected adverse reaction (SAR) implies a lesser degree of certainty about causality than adverse reaction, which means any adverse event caused by a drug (21 CFR 312.32(a)).

For this study, a SAR will include any untoward or unfavorable medical occurrence associated with:

- Study therapy: tofacitinib
- Skin biopsy
- UVB exposure

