12.3. Grading and Attribution of Adverse Events

12.3.1. Grading Criteria

The study site will grade the severity of adverse events experienced by the study participants according to the criteria set forth in the National Cancer Institute's Common Terminology Criteria for Adverse Events (CTCAE) 5.0. This document (referred to herein as the NCI-CTCAE manual) provides a common language to describe levels of severity, to

analyze and interpret data, and to articulate the clinical significance of all adverse events. The NCI-CTCAE has been reviewed by the Protocol Chair and has been deemed appropriate for the population to be studied in this protocol.

Adverse events will be graded on a scale from 1 to 5 according to the following standards in the NCI-CTCAE manual:

- Grade 1 = mild adverse event.
- Grade 2 = moderate adverse event.
- Grade 3 = severe or medically significant.
- Grade 4 = life-threatening consequences; urgent intervention indicated.
- Grade 5 = death.

Events of Grade 2 or higher and all Grade 1 or higher COVID-19 events will be recorded on the appropriate AE eCRF for this study according to 12.4, *Collection and Recording of Adverse Events*.

For grading an abnormal value or result of a clinical or laboratory evaluation (including, but not limited to, a radiograph, an ultrasound, an electrocardiogram etc.), a treatment-emergent adverse event is defined as an increase in grade from the last assessment prior to a participant starting treatment, or from the last post-baseline value that doesn't meet grading criteria. Changes in grade from screening to Day 0, Day 1, and treatment initiation (Day 2) will also be recorded as adverse events, but are not treatment-emergent. If a specific event or result from a given clinical or laboratory evaluation is not included in the NCI-CTCAE manual, then an abnormal result would be considered an adverse event if changes in therapy or monitoring are implemented as a result of the event/result.

Liver function abnormalities will be graded using criteria from NCI-CTCAE version 4.0, defined relative to the ULN as follows:

- Aspartate aminotransferase [AST] increased
 - Grade 1: > ULN – 3.0x ULN
 - Grade 2: > 3.0x ULN - 5.0x ULN
 - Grade 3: > 5.0x ULN - 20.0x ULN
 - Grade 4: > 20.0x ULN
- Alanine aminotransferase [ALT] increased
 - Grade 1: > ULN – 3.0x ULN
 - Grade 2: > 3.0x ULN - 5.0x ULN
 - Grade 3: > 5.0x ULN - 20.0x ULN
 - Grade 4: > 20.0x ULN
- Alkaline phosphatase [ALP] increased

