12.3.2. Attribution Definitions

The relationship, or attribution, of an adverse event to the study therapy regimen or study procedure(s) will initially be determined by the site investigator and recorded on the appropriate AE/SAE eCRF. Final determination of attribution for safety reporting will be determined by DAIT/NIAID. The relationship of an adverse event to study therapy regimen or procedures will be determined using the descriptors and definitions provided in Table 12.1.

For additional information and a printable version of the NCI-CTCAE manual, consult the NCI-CTCAE web site:
<http://ctep.cancer.gov/reporting/ctc.html>.

Table 12.1 Attribution of Adverse Events

Code	Descriptor	Relationship (to primary investigational product and/or other concurrent mandated study therapy or study procedure)
Unrelated Category		
1	Not Related	The adverse event is clearly not related: there is insufficient evidence to suggest a causal relationship.
Related Categories		
2	Possibly Related	The adverse event has a reasonable possibility to be related; there is evidence to suggest a causal relationship.
3	Related	The adverse event is clearly related.

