13.4. Analysis Plan

13.4.1. Analysis Populations

The **Safety Sample (SS)** population includes all participants who receive any amount of tofacitinib.

The **Per Protocol 1 (PP1)** population includes all participants who receive any amount of tofacitinib and who complete phototests and skin biopsies at both baseline (Visits 1 and 2) and post-treatment (Visits 4 and 5) time points. Only individuals who complete at least 21 days of IP dosing will have the post-treatment phototest. The primary objective of this proof-of-concept study cannot be evaluated in individuals who do not have data at both pre- and post-treatment time points.

The **Per Protocol 2 (PP2)** population includes all PP1 participants with no protocol deviations that would impact photo sensitivity assessments. The reported major deviations will be reviewed during a masked data review to determine which participants should be excluded from the PP2 population.

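### The planned adverse-event summary omits UVB and biopsy reactions that start before the first dose, and no rule separates drug from procedure attribution after it

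*Combined protocol and SAP*

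**What the plan says.** Five parts of the combined protocol and SAP bear on this.

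- **Population.** The Safety Sample "population includes all participants who receive any amount of tofacitinib" (13.4.1), and 13.4.4 adds: "Analysis of secondary safety endpoints will be conducted using the safety population".
- **Summary.** The only adverse-event summary described is in 13.4.4.3: "Treatment-emergent AEs and SAEs will be summarized by severity, by relationship to study drug, and by MedDRA Organ Class and Preferred Term". A separate item there tabulates laboratory grade increases during the study.
- **Timing.** "Tofacitinib will be distributed to eligible participants at Visit 2 (Day 1) and the first dose will be taken on Day 2" (3.1). UVB is given at Visit 1 (Day 0). Biopsies follow a day later: "On Visit 2 (Day 1), 3 biopsy sites on the right buttock include (1) unexposed skin", with two UVB-exposed sites beside it (8.5.5).
- **Status of procedure reactions.** Section 12.2.2 says "a SAR will include any untoward or unfavorable medical occurrence associated with" tofacitinib, skin biopsy or UVB exposure. Under 12.4.1, procedure-related events are collected from consent. Under 12.3.1, graded changes between screening and treatment initiation "will also be recorded as adverse events, but are not treatment-emergent".
- **Attribution.** The single relationship column of Table 12.1 (12.3.2) is headed "Relationship (to primary investigational product and/or other concurrent mandated study therapy or study procedure", with three levels. The minimum initial SAE report in 12.5.2 asks for the relationship to tofacitinib.

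The adverse-event incidence endpoint (item 7 in 3.3) is limited neither to treatment-emergent events nor to dosed participants.

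**The concern.** The trial exposes participants to three things that the protocol recognises as possible causes of harm: the drug, the UVB series and the punch biopsies. The summary is built around the drug alone. A burn or biopsy-site reaction that begins before Day 2 is collected but has no table to go into. The same kind of reaction after Day 2 does have a table, whose relationship split is labelled as drug relationship although the scale defined for the investigator covers drug and procedure together.

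The second part matters because the listed risks overlap. Cellulitis is among the serious infections listed for tofacitinib (5.1), and skin infection is a listed biopsy risk (5.4). With one open-label arm, no control group can show afterwards which cause was at work. A reader of the results could see too few procedure reactions and, depending on how the form was completed, some procedure reactions presented as drug-related.

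**Working it through.** No stated figure in the plan depends on this point, so there is none to reproduce. The check sets the rules against the schedule and then sizes the pre-dose part.

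**Step 1. Follow one event through the rules.**

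| Event (Grade 2 or higher, non-serious) | Recorded? | In Safety Sample? | Treatment-emergent? | In the 13.4.4.3 AE summary? |
|---|---|---|---|---|
| UVB or biopsy reaction starting Day 0–1, later dosed | Yes (12.4.1) | Yes | No | No |
| Any event in a person phototested at Visit 1, never dosed | Yes | No | Not applicable | No |
| Day 1 biopsy site infected on, say, Day 5 | Yes | Yes | Yes | Yes, under a drug-relationship split |
| Reaction to the Visit 4 UVB or Visit 5 biopsy | Yes | Yes | Yes | Yes, under a drug-relationship split |

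The treatment-emergent column needs a qualification. The definition in 12.3.1 is written for abnormal values or results of clinical or laboratory evaluations. For a burn or an infected wound, the answer rests on the ordinary meaning of the term.

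The laboratory tabulation does not fill the first two rows. It concerns laboratory grades, and Table 8.2 schedules no clinical laboratory tests at Visits 1 or 2.

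**Step 2. Share of procedures before dosing.** Inputs: UVB at Visits 1 and 4; three biopsies at each of Visits 2 and 5 (8.5.5, Table 8.2); first dose on Day 2; 10 completers.

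- UVB sessions: 10 × 1 = 10 before dosing, of 10 × 2 = 20 in all (50%).
- Biopsies: 10 × 3 = 30 before dosing, of 10 × 6 = 60 in all (50%).

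Upper bound, by assumption: all 18 non-safety replacements permitted in 11.3 are used, and each replaced person left after Visit 2 without a dose.

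- UVB sessions: 10 + 18 = 28 before dosing, of 28 + 10 = 38 (74%).
- Biopsies: 28 × 3 = 84 before dosing, of 84 + 30 = 114 (74%).

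These are shares of procedures, not of harms.

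**Step 3. Chance that the omitted part is not empty.** The documents give no rate. Let p be an assumed per-person risk of a recordable procedure event starting on Day 0–1. Then P(at least one in 10) = 1 − (1 − p)^10:

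| Assumed p | P(at least one in 10) |
|---|---|
| 2% | 18% |
| 5% | 40% |
| 10% | 65% |
| 20% | 89% |

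**Step 4. Attribution.** Section 12.3.2 directs that relationship to regimen or procedures be determined with Table 12.1. Section 13.4.4.3 tabulates relationship to study drug. No sentence says how the first becomes the second. An event coded Related because of a biopsy fits the table's wording and, with no conversion rule, could be counted as related to drug.

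**The case against.** The strongest reply is that the safety objective (2.3) concerns the tofacitinib regimen, so a dosed population and treatment-emergent events are the right choice, and pre-dose events would contaminate the answer. That stands, and the Safety Sample should be kept. It does not explain why an unrestricted endpoint has no table for its pre-dose part. The same objective also needs drug attribution free of procedure events.

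Other points narrow the concern:

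- A reader might infer that these events are lost altogether. They are not. They are recorded in EDC (12.4.1), compiled monthly for the medical monitor (12.8.1) and listed for the DSMB with all reported events (12.8.2.1). Repeated Grade 3 or higher events related to treatment or procedures can trigger an ad hoc review (12.8.2.2). Only the planned summary lacks them.
- A reader might infer that the eCRF holds a single relationship field. The form is not shown, the table heading says and/or, and 12.5.2 asks for the tofacitinib relationship on SAEs. Separate entries may exist.
- The pre-dose window is short, about two days after UVB and one day after biopsy, and only Grade 2 or higher events are recorded (COVID-19 events from Grade 1). Later wound infection or lingering rash would count as treatment-emergent.
- The replacement limits in 11.3 might be read as the number of people left out. They cap total entry and cover people who were dosed. The never-dosed are those who miss Visit 2, do not start, or are caught in the dosing halt of 12.8.2.2.1; no rate is given for any of these.
- The phrase in 13.4.4.3 could mean treatment-emergent AEs plus all SAEs, so the claim about the never-dosed is limited to non-serious events.

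**Conclusion.** The point holds as a gap in planned reporting. Recordable UVB and biopsy reactions starting on Day 0–1, and non-serious events in anyone phototested but never dosed, appear in no planned summary table. Half of completers' UVB sessions and biopsies fall in that pre-dose period, and at most 74% do under the extreme assumption about undosed replacements. How many events this involves cannot be known from the documents. Serious pre-dose events in dosed participants may or may not be included, depending on how 13.4.4.3 is read.

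The attribution part is a risk, not an established error. It depends on whether the eCRF separates drug from procedure, which the documents do not show. A reader might go further and conclude that the incidence endpoint will certainly be too low for procedures and too high for the drug; the text does not support that.

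The conclusion assumes that treatment-emergent carries its usual meaning for clinical events. Sample size, power, the Type 1 error rate and DSMB oversight are not affected. It is an inexpensive improvement worth making before the tables are programmed.

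**What to change.** 1. Keep the Safety Sample for tofacitinib safety. Add one table or listing of adverse events in everyone with a Visit 1 UVB exposure, split into onset before first dose and onset from first dose.
2. For each AE and SAE, record relationship to tofacitinib and relationship to UVB exposure or biopsy separately. Summarise drug-related events by the first field and procedure-related events by the second. If the eCRF already does this, say so in 12.3.2 and 13.4.4.3.
3. Reconcile 3.3, 12.3.1 and 13.4.4.3. Define treatment-emergent for clinical events as well as for abnormal values, say whether all SAEs or only treatment-emergent ones are summarised, and state which events make up the incidence endpoint.

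The cost is a few sentences of protocol and SAP text, one extra table or listing and, if not already present, one extra eCRF field. No visit, procedure or sample size changes.
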